### **13.2. Laboratory Efficacy Assessments**

There are no specific laboratory tests but it is the responsibility of the investigator to perform routine tests and to monitor the relevant results in order to evaluate the effects of the ongoing treatment with Peg-IFN.

## **14. SAFETY ASSESSMENTS**

### **14.1. Clinical Safety Assessments**

The following safety assessments are provided by the clinical protocol (Refer to Section 4.2 for the relevant timing):

- Medical History
- Physical examinations
- Vital sign measurements: temperature, pulse rate, systolic and diastolic blood pressure, and respiratory rate
- Weight
- Concomitant therapy and procedure recording
- AE and SAE (including laboratory abnormalities), pregnancy and cases of overdose recording

In addition, routine clinical assessments will be performed in order to check the safety of the Peg-IFN ongoing treatment.

### **14.2. Laboratory Safety Assessments**

At the Investigator's discretion, the following routine laboratory tests can be carried out, in order to monitor the safety profile of the ongoing treatment based on Peg-IFN:

- Hematology: RBC- WBC –Haemoglobin- Haematocrit- MCV- MCH – MCHC - Platelets Count –Lymphocytes- Monocytes – Neutrophils – Eosinophils – Basophils
- Blood chemistry: creatinine, blood urea nitrogen (BUN), alkaline phosphatase, ALT, AST, gamma-glutamyl-transferase (GGT).

A pregnancy hCG test (blood sample) will be performed at the baseline visit (T0) to exclude pregnancy, if applicable (it is not required if the subject is post-menopausal or surgically sterilized).

Refer to Section 4.2 for the timing of assessments.

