*Statistical Methods:* Descriptive statistics of T0, T1 and T2 values, of all the collected variables as well as the relevant changes from baseline will be presented as mean, and standard deviations, along with median values and ranges. The primary endpoint (change of TSQM-9 convenience domain at week 12) will be analyzed by a repeated measures analysis of variance adjusted for baseline factors (age, sex, disease duration, previous treatment duration, EDSS). The same technique will be adopted also for the analysis of the other endpoints. Correlations between variables will be assessed through the Spearman rank correlation coefficient.

*Interim Analysis:* No interim analysis will be performed.

*Sample Size Determination:* Data for estimating the sample size were derived from studies reporting the distribution (mean value and standard deviation) of the TSQM-9 in MS patients treated with IFN (9). Assuming an average value of the overall convenience domain at baseline of 55 (SD=16), 250 subjects allow a power of 90% to detect a change of 3 points on the overall convenience domain (from 55 to 58) under the conservative hypothesis of a SD=16 for the difference between baseline and week 12.

However, by assuming a drop-out rate up to 10% during the study, we consider it appropriate to enrol a total of 275 patients.

CONFIDENTIAL

The information contained herein may not be used, disclosed, or published without the written consent of Biogen Italia

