## 4.2. Schedule of Events

Tests and assessment	T0 (Enrollment)	T1 (12 weeks) ± 1 week	T2 (24 weeks) ± 1 week	ET Early termination
Inclusion/Exclusion criteria	X			
Informed consent	X			
Social-demographics (e.g., age, gender)	X			
Medical history (e.g., disease duration, previous disease history and treatments)	X			
On-treatment medical information (e.g., concomitant therapies, comorbidities)	X	X	X	X
Pregnancy hCG test	X			
Clinical and neurological evaluation (including recording of relapses and EDSS)	X	X	X	X
Drug Supply	X	X		
Assessment of patients' satisfaction (TSQM-9)	X	X	X	X
Assessment of patients' adherence	X	X	X	X
Assessment of patients' injection-system satisfaction (Adapted MSTCQ)	X	X	X	X
Assessment of patients' HRQoL (MusiqoL)	X	X	X	X
Assessment of patients' fatigue (FSS)	X	X	X	X
Routine Laboratory tests	X	X	X	X
Adverse events, pregnancy exposure, episodes of overdose		X	X	X
Drug Accountability 		X	X	X

1. If a dose is missed, it should be administered as soon as possible, within 7 days.

CONFIDENTIAL

The information contained herein may not be used, disclosed, or published without the written consent of Biogen Italia

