#### **6.2.2. Secondary Endpoints**

- Changes from baseline in the score of all domains of TSQM-9 at 24 weeks;
- Changes from baseline in patient adherence to study treatment survey at 12 and 24 weeks;
- Changes from baseline in the score of FSS (Fatigue Status Scale) at 12 and 24 weeks;
- Changes from baseline in the score of Adapted Sclerosis Treatment Concerns Questionnaire (MSTCQ) at 12 and 24 weeks;
- Changes from baseline in the score of Multiple Sclerosis International Quality of Life questionnaire (MusiQoL) at 12 and 24 weeks;

- Changes from baseline in clinical measures (ARR, percentage of relapse-free patients), measures at 24 weeks.
- Incidence and severity of adverse events occurred during the study (including local tolerance to treatment at the injection site).
- Abnormalities in laboratory values.

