### **14.3. Product-Specific or Study-Specific Safety Assessments**

Being this a Phase IV study, the investigational treatment will be administered according to the SMPC indications as done for routine practice and thus no additional specific tests are foreseen under this protocol.

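### No planned laboratory table counts patients who were normal at T0 on their previous interferon and became abnormal on Peg-IFN (minor)

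*Protocol*

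**What the plan says.** Protocol 6.2.2 lists "Abnormalities in laboratory values" among the secondary endpoints; the synopsis and 16.1.2 repeat it. Under inclusion criterion 5 (8.1), all patients enter on an injectable subcutaneous interferon.

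**Collection.** The schedule in Protocol 4.2 marks "Routine Laboratory tests" at T0, T1, T2 and ET, with no footnote. Section 14.2 introduces its panel of 13 haematology and 6 chemistry analytes with "At the Investigator's discretion, the following routine laboratory tests can be carried out" and closes with "Refer to Section 4.2 for the timing of assessments". SAP section 8 repeats the discretionary sentence. Section 13.2 states: "There are no specific laboratory tests but it is the responsibility of the investigator to perform routine tests". Section 14.3 says that "no additional specific tests are foreseen under this protocol".

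**Reporting.** Protocol 16.4.2 and SAP 12b plan descriptive statistics for the tests performed and a tabulation of abnormalities judged against the laboratory's normal ranges. SAP 13 turns this into two outputs, repeated by visit where applicable. P36 is a count and percentage of abnormalities for each test. P37 is a listing of the abnormal results. The synopsis (Statistical Methods) adds that descriptive statistics "of all the collected variables as well as the relevant changes from baseline will be presented".

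**The concern.** Each patient moves from one interferon to another. An abnormal liver enzyme or blood count at week 12 may have arisen on Peg-IFN, or may have been there already under the previous interferon. The laboratory question that a switch study can answer is how many patients were normal before the switch and abnormal after it.

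P36 does not ask that question. It gives the proportion abnormal at each visit, and two such proportions side by side do not show whether the same patients are abnormal at both.

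The gap deserves attention here for two reasons in the protocol itself. Section 5.1 says that no efficacy or safety study data exist from patients switching between non-pegylated and pegylated interferon. Section 15.3.3 names liver, kidney and blood problems as possible serious effects, and these are the areas that the 14.2 panel covers.

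A smaller matter goes with it. The analytes are at the investigator's choice, so the number of patients behind each percentage may vary from test to test, and P36 does not show it.

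**Working it through.** The plan gives no laboratory figure to reproduce. The check is a reading of the planned outputs, followed by illustrations. All testing and abnormality rates below are assumptions.

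**Step 1. Does any planned output count new abnormalities?**

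| Output | What it gives | Does it count patients normal at T0 and abnormal later? |
|---|---|---|
| P36, by visit | Abnormalities per test | No. Proportion abnormal at each visit only |
| P37 | Listing of abnormal results | No. A patient not listed at T0 may be normal or untested |
| Descriptive statistics and change from baseline (16.4.2, SAP 12b, synopsis) | Summaries of values | No. They do not count patients |
| Adverse-event tables (16.4.2, P38) | Type, incidence, severity, relatedness | No. There is no split by T0 laboratory status |
| P39 | Adverse-event listing; onset dates are recorded under 15.6 | Only by reading the listing case by case, for abnormalities reported as events |

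No other table in P1 to P41 addresses laboratory values.

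**Step 2. What P36 leaves open.** Let n patients be tested at both T0 and T1, with a abnormal at each visit. If all T0 abnormalities persist, there are 0 new cases. If all resolve and are replaced, there are a new cases among the n − a who were normal at T0. The upper limit is a/(n − a). Take n = 225, which is 90% of the 250 patients used in Protocol 16.5.

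| Assumed share abnormal at both visits | a | n − a | New among those normal at T0 |
|---|---|---|---|
| 4% | 9 | 216 | 0 to 9 (0% to 4.2%) |
| 12% | 27 | 198 | 0 to 27 (0% to 13.6%) |
| 20% | 45 | 180 | 0 to 45 (0% to 25%) |

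With 175 or 125 tested and 12% abnormal, the ranges are 0 to 21 of 154 and 0 to 15 of 110, again 0% to 13.6%. In each row the two P36 percentages are identical whatever the true number of new cases. The upper limits are extremes, not expectations.

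**Step 3. The same new risk under different T0 levels.** Let b be the proportion abnormal at T0 and i the risk of becoming abnormal among those normal at T0. If T0 abnormalities persist, the proportion abnormal at the later visit is b + (1 − b) × i. With i = 5%:

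- b = 0%: 5%.
- b = 10%: 0.10 + 0.90 × 0.05 = 14.5%, of which 0.90 × 0.05 = 4.5% of all patients are new.
- b = 20%: 0.20 + 0.80 × 0.05 = 24%.

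If half of the T0 abnormalities resolve, the last two become 0.05 + 0.045 = 9.5% and 0.10 + 0.04 = 14%.

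**Step 4. Mean change does not fill the gap.** If a share of patients rises by one upper limit of normal, the mean moves by that share of the limit: 0.02, 0.05 or 0.10 for 2%, 5% or 10% of patients. It moves by 0 if as many patients fall by the same amount.

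**Step 5. Why the number tested is worth printing.** Suppose 20 patients have a given abnormality. Out of about 275 treated (synopsis) this is 20/275 = 7.3%. Out of those tested it is 20/220 = 9.1% if 80% are tested, 20/165 = 12.1% at 60%, and 20/110 = 18.2% at 40%. If all are tested, the two bases agree.

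**The case against.** The strongest reply is that emergence is already partly covered. P36 is repeated by visit, so T0 stands beside T1 and T2. Changes from baseline are promised for all collected variables. Under 15.1.2 an abnormal laboratory finding can be an adverse event, and events are tabulated and listed, with onset dates recorded. All this is true, but Step 1 shows that none of it yields a count of patients who went from normal to abnormal. The adverse-event route also depends on the investigator reporting the finding. The two start points for event recording in 15.2.2 (first dose and consent) are a separate drafting matter and carry no weight here.

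A reader might go further and infer from 14.2 that testing is optional, so that the endpoint may go uncollected. The documents do not support that. Section 4.2 schedules the tests at four visits, 14.2 refers back to it, and 13.2 makes routine testing the investigator's responsibility. The synopsis includes laboratory abnormalities among the evaluations made at every timepoint. The natural reading is that blood is tested at the scheduled visits and the investigator chooses the analytes. For a marketed product used as in routine practice (14.3), that looks deliberate.

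The missing denominator can also be overstated. SAP 12b speaks of tests performed, and SAP 9 applies no imputation to laboratory values, so patients tested is the likely base. That leaves a missing detail, not an error. The safety set in 16.4.1 does not require a laboratory result, however, so it is still worth stating the base.

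Finally, every rate in the illustrations is assumed, and the new-case ranges start at zero. That objection stands: the calculations show what P36 cannot distinguish, not what will happen in this trial.

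**Conclusion.** The point holds as a minor one. No planned table separates laboratory abnormalities carried over from the previous interferon from those that arise on Peg-IFN, in a study where every patient switches. The conclusion rests on the text of the SAP table list and of the two laboratory analysis sections, not on any assumed rate.

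Its size in this trial is unknown. On the assumed ranges, unchanged P36 percentages of 4%, 12% or 20% would be compatible with new-abnormality rates of 0% up to 4.2%, 13.6% or 25%.

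Two stronger conclusions are not supported. One is that the laboratory percentages will be biased because the investigator chooses the analytes: the patients tested for an analyte may be a selected subset, but the documents give no direction or size, and the bias may be zero. The other is that all 19 analytes must be made mandatory. That would reverse an apparently deliberate choice, and the gap in P36 can be closed without it. The primary endpoint is unaffected.

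**What to change.** Revise P36 in SAP 13, with a matching sentence in SAP 12b. For each test and visit, report:

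1. the number of patients tested;
2. the number and percentage abnormal out of those tested;
3. among patients tested and normal at T0 who also have a result at the later visit, the number and percentage newly abnormal at T1, T2 or ET.

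The cost is one revised table from data already collected. It needs no extra blood test or visit, and no change to the protocol text, so no amendment under Protocol 19.3. The number tested shows what each percentage rests on even if discretion over analytes is kept.

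The sponsor may separately wish to align 14.2 and SAP 8 with 4.2 by fixing the panel. That is optional. It would also mean adjusting 13.2 and 14.3, an ethics committee submission, and some added tests at sites that would have skipped them.

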### **14.3. Product-Specific or Study-Specific Safety Assessments**

Being this a Phase IV study, the investigational treatment will be administered according to the SMPC indications as done for routine practice and thus no additional specific tests are foreseen under this protocol.

## **15. SAFETY DEFINITIONS, MONITORING AND REPORTING**

Throughout the course of the study, every effort must be made to remain alert to possible AEs. If an AE occurs, the first concern should be for the safety of the subject. If necessary, appropriate medical intervention should be provided.

At the signing of the ICF, each subject must be given the names and telephone numbers of study site staff for reporting AEs and medical emergencies.

### **15.1. Definitions**

#### **15.1.1. Serious Pretreatment Event**

A serious pretreatment event is any event that meets the criteria for serious adverse event (SAE) reporting (as defined in Section 15.1.3) and occurs after the subject signs the ICF, but before administration of study treatment.

#### **15.1.2. Adverse Event**

An AE is any untoward medical occurrence in a patient or clinical investigation subject administered a pharmaceutical product and that does not necessarily have a causal relationship with this treatment. An AE can therefore be any unfavorable and unintended sign (including an abnormal laboratory finding), symptom, or disease temporally associated with the use of a medicinal (investigational) product, whether or not related to the medicinal (investigational) product.

#### **15.1.3. Serious Adverse Event**

An SAE is any untoward medical occurrence that at any dose:

- results in death
- in the view of the Investigator, places the subject at immediate risk of death (a life-threatening event); however, this does not include an event that, had it occurred in a more severe form, might have caused death
- requires inpatient hospitalization or prolongation of existing hospitalization
- results in persistent or significant disability/incapacity, or
- results in a congenital anomaly/birth defect.

A SAE may also be any other medically important event that, in the opinion of the Investigator, may jeopardize the subject or may require intervention to prevent one of the other outcomes listed in the definition above. (Examples of such medical events include allergic bronchospasm requiring intensive treatment in an emergency room or convulsions occurring at home that do not require an inpatient hospitalization.)

In addition, terms listed on the Biogen Medically Significant Terms List should always be considered SAEs based on medical judgment (Appendix G).

## **15.2. Monitoring and Recording Events**

### **15.2.1. Serious Pretreatment Events**

A serious pretreatment event experienced by the subject after signing and dating the ICF, but before administration of study treatment is to be recorded on the e-CRF and on the SAE Form, and faxed or sent by email to Biogen Italia Drug Safety Unit within 24 hours of the study site staff becoming aware of the event (see Section 15.2.5).

### **15.2.2. Adverse Events**

Any AE experienced by the subject between the time of first dose of study treatment and the end of the study is to be recorded on the e-CRF, regardless of the severity of the event or its relationship to study treatment.

Any AE experienced by the subject between the time of signing the ICF and the end of the study is to be recorded on the e-CRF, regardless of the severity of the event or its relationship to study treatment.

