The following activities will be performed at all the study timepoints (T0, T1 and T2):

1. registration of concomitant diseases;
2. registration of concomitant medications;
3. evaluation of clinical and neurological (EDSS) conditions, adherence to treatment, occurrence of any adverse events and/or laboratory parameters abnormalities.

Moreover, at each visit patients will be administered the study questionnaires in order to evaluate:

1. Patients' satisfaction (TSMQ-9 test);
2. Patients' injection-system satisfaction (adapted MSTCQ test);
3. Patients's quality of life (MusiQoL test);
4. Patients' fatigue (FSS test).

Questionnaires will be completed electronically, by means of an i-PAD that provided by the Sponsor to the centers involved in the study. Patients unable to complete the electronic format will be supplied with paper hard copies of the questionnaires, in order to ensure proper data collection.

CONFIDENTIAL

The information contained herein may not be used, disclosed, or published without the written consent of  
Biogen Italia

**Rationale for Dose and  
Schedule Selection:**

Peg-IFN beta-1a (Plegridy®) is a solution for subcutaneous injection in pre-filled pen and will be administered fortnightly at a dose of 125 mcg.

The treatment involves a dose titration phase followed by a maintenance phase, according to the following scheme:

Titration phase:

Plegridy® 63 micrograms on day 1 of treatment

Plegridy® 94 micrograms on day 14, i.e. two weeks after the first dose.

Maintenance phase:

Plegridy® 125 micrograms on day 28 after the first dose and then every two weeks.

Patients will thus start treatment with 63 micrograms at dose 1, increasing to 94 micrograms at dose 2, reaching the full dose of 125 micrograms by dose 3 and continuing with the full dose (125 micrograms) every 2 weeks thereafter.

The total duration of treatment will be of 24 weeks (titration phase and maintenance phase).

Every effort should be made to administer Plegridy® at the same time and at the same day of the week.

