## **7. STUDY DESIGN**

### **7.1. Study Overview**

This is a 6 month, phase IV, open-label, single-arm, interventional, multicentric study, based on self-administered questionnaires (as described in Methods) and aimed at evaluating patient-reported effects on user's satisfaction of Peg-IFN beta-1a therapy on patients unsatisfied with other injectable, subcutaneous Interferons. The relevant evaluations will be performed at baseline, week 12 and week 24.

Informed consent will be obtained at baseline prior to study enrolment and before collection of all relevant clinical information (i.e., relapses, EDSS).

Clinical evaluation and questionnaire administration will be performed at baseline (within 2 weeks before Peg-IFN beta-1a therapy onset) and after 12 and 24 weeks.

Subjects may elect to discontinue from study treatment at any time, due to medical reasons (contraindications, medical conditions that necessitate drug discontinuation according to the Investigator) or at personal and/or Investigator's discretion. In all cases, reasons for discontinuation from investigational treatment or withdrawal from the study will be recorded in the subject's CRF.

All relevant and required information about any adverse event (serious and non-serious), including laboratory abnormalities and about pregnancy and cases of overdose occurring during the study will be collected and registered in the subject's CRF.

In case of SAE, pregnancy, or cases of overdose, the Investigator will have to notify Biogen Italia Srl's Drug Safety Unit immediately and no later than 24 hours from its occurrence, by fax or e-mail. Any event follow-up will have to be notified to Biogen Italia's Drug Safety Unit within 24 hours from its recording.

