The primary endpoint is to evaluate the changes from baseline in the score of convenience satisfaction domain of TSQM-9 at 12 weeks. (*Stata instruction: anova var1 time, repeated(time)*)

b. Secondary Endpoints Analysis

- Changes from baseline in the score of all domains of TSQM-9 at 24 weeks;
- Changes from baseline in patient adherence to study treatment survey at 12 and 24 weeks;
- Changes from baseline in the score of FSS (Fatigue Status Scale) at 12 and 24 weeks;
- Changes from baseline in the score of Adapted Sclerosis Treatment Concerns Questionnaire (MSTCQ) at 12 and 24 weeks;
- Changes from baseline in the score of Multiple Sclerosis International Quality of Life questionnaire (MusiQoL) at 12 and 24 weeks;
- Changes from baseline in clinical measures (ARR, percentage of relapse-free patients), measures at 24 weeks.

All the above primary and secondary endpoints will be analysed by a repeated measures analysis of variance adjusted for baseline factors (age, sex, disease duration, previous treatment duration, EDSS) (*Stata instruction: anova var1 var2 time, repeated(time)*).

Correlations between variables will be assessed by a Spearman rank correlation coefficient (*Stata instruction: spearman var1 var2*).

[figure not shown]
To evaluate the relationship between patients' satisfaction and social-demographic factors (age, sex, employment working, level of education, etc.) and clinical characteristics (ARR, disability, etc.) generalized linear mixed models for repeated measurements will be performed (*Stata instruction: mixed var1 var2 || patient:*).

12. Safety Data

a. Adverse events

All events will be coded using the Medical Dictionary for Regulatory Activities (MedDRA). Type and incidence of all AEs will be tabulated. Severity and drug relatedness of all reported AEs will be tabulated.

b. Clinical Laboratory Tests

	Statistical Analysis Plan Protocol N. BIIT0215– Platinum	Pag. 14 di 18
---	---	---------------

For the clinical laboratory data, descriptive statistics will be generated for all tests performed. Laboratory abnormalities will be determined in accordance with the normal ranges of the clinical laboratory. Laboratory abnormalities will be tabulated.

13. Tables

The following tables will be repeated for each visit, if applicable.

- P1. Number and percentage of patients enrolled per center
- P2. Number and percentage of patients stratified by gender; mean and median age, range and interquartile range;

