P21. Number and percentage of patient who have correctly taken the prescribed doses of treatment within the last 28 days; if don't, mean and median, interquartile range and range of injections have not been performed during the last 28 days;

P22. Number and percentage of patients per reasons to non correctly taken the treatment:

- a) Anxiety for injection
- b) Skin reaction
- c) Forgot to take the dose
- d) Pain at the injection site

- e) Depression
- f) Headhache
- g) Fatigue
- h) Flu-like symptoms
- i) “I did not want to”
- j) “I am not sure of the benefits”
- k) “I am tired of injections”
- l) No one available for injection
- m) Uncomfortable dosing
- n) “I am pregnant / I have planned a pregnancy”
- o) Other

- P23. Mean and median, interquartile range and range of injections expected from the therapy taken in the last 28 days;
- P24. Mean and median, interquartile range and range of MSTCQ;
- P25. Change from baseline in the score of the MSTCQ at 12 and 24 weeks;
- P26. Adjusted repeated measures analysis of variance for change of the MSTCQ at 12 and 24 weeks;
- P27. Mean and median, interquartile range and range of MusiQol;
- P28. Change from baseline in the score of the MusiQol at 12 and 24 weeks;
- P29. Adjusted repeated measures analysis of variance for change of the MusiQol at 12 and 24 weeks;
- P30. Mean and median, interquartile range and range of FSS;
- P31. Change from baseline in the score of the FSS at 12 and 24 weeks;
- P32. Adjusted repeated measures analysis of variance for change of the FSS at 12 and 24 weeks;
- P33. Mean and median, interquartile range and range of EDSS;
- P34. Change from baseline in the score of the EDSS at 12 and 24 weeks;
- P35. ARR, Annualized Relapse Rate
- P36. Number and percentage of abnormalities in laboratory values per each test;
- P37. List of all laboratory abnormalities;
- P38. Number and percentage of adverse events stratified by severity;

	
Statistical Analysis Plan Protocol N. BIIT0215– Platinum
	
Pag. 18 di 18

--	---	---

- P39. List of all adverse events with related characteristics;
- P40. Number and percentage of patients who discontinued the study and reasons of discontinuity;
- P41. Number and percentage of patients who experienced pregnancy during the study and outcome of pregnancy.

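### AE recording starts at first dose in one sentence and at consent in the next, and the AE tables have no onset limit, so non-serious pre-dose events can enter the Peg-IFN tables

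*Protocol*

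**What the plan says.** **Collection.** Protocol Section 15.2.2 has two consecutive sentences that differ only in their start point. The first covers "Any AE experienced by the subject between the time of first dose of study treatment and the end of the study"; the second covers "Any AE experienced by the subject between the time of signing the ICF and the end of the study". The synopsis (Section 3) places evaluation of the "occurrence of any adverse events and/or laboratory parameters abnormalities" at T0, T1 and T2. The schedule of events (Section 4.2) has a row for "Adverse events, pregnancy exposure, episodes of overdose" that is marked at T1, T2 and early termination but not at T0.

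**Timing.** Section 7.1 has consent obtained at baseline and allows baseline assessments "within 2 weeks before Peg-IFN beta-1a therapy onset"; SAP Section 2 repeats this. The visit schedule in the synopsis instead equates T0 with the start of Peg-IFN. Inclusion criterion 5 requires treatment with an injectable subcutaneous interferon, and neither document says when that drug stops.

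**Analysis.** SAP Section 12.a says "Type and incidence of all AEs will be tabulated" and "Severity and drug relatedness of all reported AEs will be tabulated", in line with Protocol 16.4.2. Table P38 is "Number and percentage of adverse events stratified by severity". None of these limits events by onset date, and neither document defines a treatment-emergent event. Incidence and severity of AEs, with local tolerance at the injection site, is a secondary endpoint (Section 6.2.2).

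**The concern.** With consent as the start point, recording opens while the patient may still be using the previous interferon. Reactions in that interval resemble those expected of Peg-IFN. Section 10.1 describes flu-like symptoms as something seen on starting interferons generally. The MSTCQ, described in Section 13.1 as covering concerns with IFN-beta treatment, has subscales for injection-site reactions and flu-like symptoms. Section 15.3.3 lists injection-site damage and flu-like symptoms among the events expected with Peg-IFN. Once tabulated without an onset limit, a pre-dose event looks the same as a Peg-IFN event.

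The study has one arm, so no control group would show the same background. Any pre-dose event that is counted raises the reported Peg-IFN figures or leaves them unchanged. The two sentences also let sites work to different windows, in which case the rates would depend partly on which sentence a site followed.

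**Working it through.** The plan states no figure on this point, so there is nothing to reproduce. The check sets the passages side by side and then bounds the exposed time.

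**1. Is the start point settled elsewhere?** No. The synopsis has AE evaluation at T0 and the schedule of events does not mark it. The rules for serious events do not settle it either. Section 15.2.1 covers serious events from consent to first dose and 15.2.3 covers them from first dose. Together they agree with the consent start in 15.2.5, so they are consistent with each other and say nothing about non-serious events.

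**2. Does the analysis remove pre-dose events?**
- The safety population (Protocol 16.4.1) and the FAS (SAP Section 5) require at least one dose. That restricts which patients count, not which events.
- Protocol 16.4.2, SAP 12.a and table P38 carry no onset limit.
- The causality definitions in Section 15.3.1 give onset before drug administration as an example pointing to not related. This protects the relatedness table, but not overall type, incidence or severity.
- Serious pre-dose events have a category of their own (15.1.1, 15.2.1). Non-serious ones have none.

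**3. How long is the exposed window?** Inputs:
- Gap from consent/baseline to first dose: 0 days if T0 is the start of treatment (synopsis visit schedule), up to 14 days under Section 7.1.
- Treatment period: 24 weeks × 7 = 168 days (synopsis).

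Pre-dose share of the recording period = gap / (gap + 168):

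| Gap (days) | Calculation | Share |
|---|---|---|
| 0 | 0/168 | 0% |
| 7 | 7/175 | 4.0% |
| 14 | 14/182 | 7.7% |

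These shares are for a patient followed for the nominal 24 weeks. For a patient who stops early, the same 14-day limit is a larger part of a shorter period.

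**4. Direction of the effect on patient incidence.** Let p be the share of patients with an AE on or after first dose and q the share with one between consent and first dose. If the two are independent, incidence in the consent-based window is p + q(1 − p), an excess of q(1 − p). The excess cannot be negative. The documents give neither p nor q, so the calculation stops here.

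**The case against.** The strongest reply is that the two sentences overlap rather than exclude each other. Neither says only, so a site obeying both records from consent, and events since consent can be collected at T1 even though the schedule has no mark at T0. That stands as a reading, but it leaves the synopsis and schedule unaligned and does nothing for the analysis, where all recorded events are tabulated.

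A second reply is that there may be no gap: the synopsis equates T0 with the start of treatment, and drug is dispensed at T0. This also stands in part. The gap may be near zero for many patients, which is why the range starts at 0. Section 7.1 and SAP Section 2 nevertheless permit 2 weeks, and Section 15.1.1 defines an interval between consent and first dose.

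A third reply is that safety is descriptive, onset dates must be determined for every event (Section 15.6), P39 lists each event with its characteristics, and an analyst could filter. It is true that no test, sample size or primary result is touched. The written rule, however, is to tabulate all AEs, and the SAP says its results are for publication. A filter chosen after the data are seen would not be pre-specified.

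In the other direction, a reader might infer from the injection frequencies in the introduction (3 to 4 a week for subcutaneous interferons, against one every 2 weeks for Peg-IFN) that a large part of the reported events could belong to the old drug. The documents do not support that. Injections are neither events nor patients, no per-injection event rate is given, and the inference also needs the full 2-week gap with the old drug taken up to the switch. Nor do the documents show that sites did in fact use different windows; they only leave that possible.

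**Conclusion.** The point holds as a drafting inconsistency combined with a missing analysis definition. As written, the plan lets non-serious events from before the first dose enter the overall type, incidence and severity tables for Peg-IFN. The exposed window is 0 to 14 days per patient, at most 7.7% of a full 182-day recording period. The upper end assumes consent at a baseline visit a full 2 weeks before first dose; attributing such events to the previous interferon further assumes that drug was still being taken. The effect is probably modest, and its size in events or patients cannot be derived from the documents.

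A reader might go further and conclude that pre-dose events would be reported as caused by Peg-IFN. That is not supported: Section 15.3.1 points to not related for such events, and serious ones are classed separately. What is affected is a descriptive secondary endpoint in a study with no comparator. The correction is worth making because it costs little and removes a one-directional bias.

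**What to change.** 1. **Protocol 15.2.2:** keep one collection window. Consent to end of study contains both of the present ones.
2. **Synopsis and Section 4.2:** make AE collection at T0 agree with that window.
3. **Protocol 16.4.2 and SAP 12.a:** base the AE endpoint tables on treatment-emergent events, meaning onset or worsening on or after the first dose of Peg-IFN. List pre-dose events separately.

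With the onset limit in place, an event that began before first dose and did not worsen stays out of the endpoint tables whichever sentence a site followed.

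The cost is one deleted sentence, two small alignments, a definition in each document and a date filter in the tables. Onset dates are already required, so the filter needs no new data item. A worsening should be entered with its own onset date so that the filter can find it. If some sites have already recorded from first dose only, their pre-dose listing will be incomplete, and the report should say so.
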